1.3 Advantages and Disadvantages

Studies have shown that catheter ablation is a safe and effective treatment option for patients with atrial fibrillation, despite the inherent risks.^{2, 3} The Hansen System, including the family of Artisan guide catheters, provide the potential for enhanced navigation, control and stability of tissue contact at the point of ablation over manual manipulation of a commercially available ablation catheter when used in subjects with atrial fibrillation.

The Sensei® X Robotic Catheter System and the family of Artisan guide catheters are CE marked to facilitate manipulation and precise positioning of percutaneous catheters within the atria of the heart. As reflected in a wide body of literature, pulmonary vein isolation procedures and subject demographics in Europe are representative of procedures and demographics in the United States. Literature review of ablation cases done in Europe with the Sensei® X Robotic Catheter System and Artisan Guide Catheter used to manipulate marketed catheters show a similar event rate to standard percutaneous cardiovascular and ablation procedures.^{10,11,12,13}

The Sensei® X Robotic Catheter System, family of Artisan guide catheters, and accessories are 510(k) cleared to facilitate manipulation, positioning and control of both the Polaris DX and Livewire Steerable electrode catheters for mapping within the atria of the heart. To date, over 14,000 commercial procedures have been performed using the Sensei X Robotic Catheter System and family of Artisan Guide Catheters to manipulate catheters within the atria of the heart.

The Sensei® X Robotic Catheter System and family of Artisan guide catheters were extensively tested for the CE mark and 510(k) clearance. Full risk analyses have been conducted for the Hansen System for navigating a commercially available ablation catheter.

The primary risks associated with use as proposed in this study are not necessarily associated with the Hansen System, but are inherent in performing any interventional electrophysiological or ablation procedure. These risks include major adverse cardiac events (MACE) as listed in section 8.0 Risk Analysis. The MACE rates associated with the use of the Hansen System are not anticipated to be greater than those associated with manual positioning of intra-cardiac ablation catheters.

1.4 Alternatives

Alternative therapy for symptomatic paroxysmal atrial fibrillation includes the following:

- Pharmacological therapy for rate and/or rhythm control,
- Electrical cardioversion,
- Surgical intervention to create atrial lesions,
- Implantable devices to control heart rate,
- Ablation therapy with approved guide catheters.

1.5 Additional Information

Even though the Hansen System is only used to position a therapy catheter and does not provide therapy, the FDA Guidances for Industry and Staff – *Cardiac Ablation Catheters Generic Indication for Use* and *Clinical Study Designs for Percutaneous Catheter Ablation for Treatment of Atrial Fibrillation* have been referenced during the formation of this proposed study. Because the ThermoCool® catheter was initially used in the study within its indication, labeling for the ThermoCool® catheter has also been referenced for creation of the study protocol. The investigational plan also references the *2012 HRS/EHRA/ECAS Expert Consensus Statement on Catheter and Surgical Ablation of Atrial Fibrillation: Recommendations for subject Selection, Procedural Techniques, Subject Management and Follow-up, Definitions, Endpoints, and Research Trial Design*.

2.0 Purpose

2.1 Study Purpose

The purpose of this clinical study, in the United States, is to demonstrate that the family of Artisan guide catheters controlled by the Sensei® X Robotic Catheter System can safely and effectively introduce and position a commercially available RF ablation catheter for the treatment of subjects with paroxysmal atrial fibrillation. This is a post market study outside the United States, with the Artisan catheters and Sensei X System used according to CE mark and per Instructions for Use.

This study will gather data to assess the following primary study endpoints:

1. The Major Complication rates including acute events through seven days (as defined in this investigational plan) and the incidence of esophageal injury and pulmonary vein stenosis through day 180.
2. The Chronic Success rate from day 91 through day 365.

2.2 Study Objective

To evaluate the safety and effectiveness of the family of Artisan guide catheters when used to remotely introduce and position specified commercially available cardiac RF ablation catheters to treat subjects with paroxysmal atrial fibrillation.

3.0 Device Description

3.1 Device Name

Hansen Medical Sensei® X Robotic Catheter System and the family of Artisan guide catheters.

3.2 Principles of Operation

The Hansen Medical device consists of two primary components, the Sensei® X Robotic Catheter System and the family of Artisan guide catheters (remotely controlled steerable guide catheters). The physician remotely directs the movement of the Artisan Guide Catheter with the Sensei® X Robotic Catheter System.

The Sensei® X Robotic Catheter System is an electronically controlled mechanical system for remotely controlling the family of Artisan guide catheters. The Sensei® X Robotic Catheter System is comprised of a physician workstation, an electronics rack, and a subject side Remote Catheter Manipulator (RCM). The system allows the clinician to direct the catheter tip to a desired intra-cardiac location based on visual feedback from 3-D electroanatomic maps, fluoroscopic images and Intra-Cardiac Echocardiography (ICE) images while seated at the remote workstation. The RCM electromechanically manipulates the steerable guide catheter in response to commands received from the physician through a special three-dimensional joystick called the Instinctive Motion Controller (IMC) at the physician workstation (Figure 1).

Figure 1: Sensei® X Robotic Catheter Control System

The family of Artisan guide catheters consists of the Artisan and the Artisan Extend Guide Catheters (Figure 2). Each guide catheter is a conventional pull-wire actuated open-lumen guide catheter. The inner lumen is 8F diameter and the guide catheter fits through a standard 14F hemostatic introducer sheath. The guide catheters attach to the RCM (Figure 3) through a sterile drape barrier and the RCM in turn actuates the catheter pull-wires in response to commands from the physician seated at the workstation. The Artisan and Artisan Extend are guide catheters and do not have therapeutic or diagnostic capabilities on their own.

The Artisan was originally cleared with the Sensei® Robotic Catheter System under 510(k) K052480 in May, 2007 and CE marked in September 2006. The Artisan Extend, cleared under 510(k) K122275 in August, 2012 and CE marked in February, 2013, is an extension to the Artisan family of guide catheters. The navigation capabilities of these catheters are identical. The difference between the two catheters is the proximal flush assembly that remains outside of the body throughout the procedure and is the hemostatic introduction point for commercially available catheter-based devices.

Figure 2: Distal Tip Articulation of The Family of Artisan Guide Catheters

Figure 3: Artisan Catheter Attached to the RCM

The Sensei® X system also has a feature called *IntelliSense*, cleared under 510(k) K073225, that provides the physician with information about the relative level of contact force being applied through the family of Artisan guide catheters. The feature uses force sensors at the proximal opening of the Artisan Guide Catheter to grip the mapping catheter. The output from the force sensors is presented to the physician at the Sensei® X workstation in grams on an instantaneous analog graphic scale, on a running strip-chart scale and via a light, non-directional buzz on the IMC that increases as the reading increases. A sample of the IntelliSense output scale on the workstation screen is shown in Figure 4.

[figure not shown]

Figure 4: IntelliSense Displays (highlighted in yellow)

3.3 Intended Use

No changes are being made to the Sensei® X Robotic Catheter System or the family of Artisan guide catheters to execute this proposed IDE study. Data from this proposed IDE clinical study will be used to support a submission to extend the intended use to include introducing and positioning of specified commercially available RF ablation catheters for use in subjects with paroxysmal atrial fibrillation in the United States.

3.4 Ablation Catheters

The Sensei X Robotic Catheter System and Artisan guide catheters will be used in this study with commercially available cardiac RF ablation catheters that meet the following specifications¹. The following catheters will be used in the study: the Biosense Webster ThermoCool,(NaviStar, SmartTouch and Celsius), St. Jude Medical Safire, and the Boston Scientific Blazer II. If the ablation catheter does not meet the specifications below, it should not be used in the study.

72_____

¹ Catheters evaluated through bench testing included the Biosense Webster NaviStar ThermoCool, Biosense Webster Celsius ThermoCool, Biosense Webster ThermoCool SmartTouch, St. Jude Medical CoolPath, St. Jude Medical Safire BLU, St. Jude Medical Safire, and the Boston Scientific Blazer II.

- Commercially available radiofrequency cardiac ablation catheter
- Irrigated tip catheter
- Compatible with CARTO or EnSite Velocity mapping systems
- Compatible with an 8Fr sheath
- Working length ≥ 110
- Compatibility with multi-plane deflectable sheaths
- Symmetrical tip bending performance. This is observed by setting the ablation catheter in the neutral/straight position and attempting to manually deflect the tip in multiple planes. If the bending performance is symmetrical, the catheter can be used.

The investigator may choose which ablation catheter is to be used for ablation treatment, as long as the catheter meets the specifications listed.

4.0 Labeling

Copies of Instructions for Use for the Hansen Medical Sensei X System and the family of Artisan guide catheters are provided in Appendix I.

5.0 Study Design

This is a prospective, single-arm, multi-center, US and OUS study to evaluate the safety and effectiveness of the family of Artisan guide catheters with the Sensei[®] X Robotic Catheter System for introducing and positioning one of a set of specified commercially available ablation catheter in subjects with paroxysmal atrial fibrillation. Up to 14 investigational sites will participate in this study to enroll a minimum of 125 and up to a maximum of 250 subjects.

Interim analyses will be conducted starting after the first 125 subjects are enrolled, and continuing every 25 subjects thereafter. At each interim analysis, enrollment may be stopped for expected success or for futility. If there is at least 95% probability that both the safety and effectiveness analysis will meet the success criteria if enrollment stops at the current sample size and all patients are followed to the 12-month endpoint, then enrollment will stop early for expected success. Up to three additional interim analyses will be performed: after full enrollment and at 3 and 6 months after full enrollment to assess the criteria for an early declaration of success. If there is at least 99.9% probability that both the safety and effectiveness analyses will meet the success criteria after all enrolled subjects are followed to the 12-month endpoint, and if a minimum of 80 and 100 patients have complete follow-up for the effectiveness and safety endpoints, respectively, then the trial will declare early success. A clinical study report can then be prepared for submission to the FDA.

Subsequently, the final analysis will occur when the 12-month follow-up is complete for all enrolled subjects. An updated final clinical study report will then be prepared and submitted to the FDA to close out the IDE study.

Based on the interim analyses defined for the study, the maximum number of subjects allowed at any site at each interim analysis is defined in the following table.

Table 7: Maximum Subjects per Site at Each Interim Analysis

Interim Analysis Sample Size	Maximum Subjects per Site
125	25
150	30
175	35
200	40
225	45
250	50

Study subjects with symptomatic, drug-refractory paroxysmal atrial fibrillation will undergo a catheter-based ablation procedure as part of this study to eradicate the aberrant atrial rhythm. If necessary, up to two additional catheter ablation procedures within the 90-day blanking period following the initial ablation procedure may be performed.

Prior to the start of any ablation procedure, the subject's echocardiogram will be reviewed to ensure no evidence of left atrial thrombus. A routine EP study may be performed to evaluate the location, morphology, and dimensions of each pulmonary vein by venogram. Intra-cardiac echocardiography (ICE) may also be performed prior to the ablation procedure at the physician's discretion.

A subject is required to meet all the inclusion and none of the exclusion criteria to participate in the study. Enrollment occurs when a subject signs the Informed Consent Form. The subject must then meet all additional intra-procedural enrollment criteria (i.e. no intramural thrombus, etc.). If the subject does not meet all intra-procedural enrollment criteria, the subject will not be treated with the study device and will be withdrawn from the study. The screening, baseline, and withdrawal case report forms should be completed. The investigator shall report any acute procedural adverse events on the adverse event form.

These subjects who are withdrawn prior to the procedure will count against the maximum enrollment limit. However, the company requests that the maximum enrollment limit is increased accordingly to account for those who signed the Informed Consent Form but did not undergo the study procedure.

5.1 Duration of Study

Subjects will be enrolled for up to one year and have follow-up evaluations at 7 days, 30 days, 90 days, 180 days and 365 days post initial ablation procedure. All subjects will be evaluated on the day of discharge or within 48 hours (whichever comes first), at 7 days post procedure by telephone and 30 days for safety, then 90 days, 180 days, and 365 days post procedure for safety and efficacy. The total duration of the trial will be determined by the

adaptive design, and will be governed by the actual accrual rate and whether any of the pre-specified rules for early stopping are met. Expected study duration could range from 24 months to 42 months.

5.2 Primary Safety Endpoints

The primary safety endpoint is defined as the incidence of Major Complications, as defined below:

Major Complications during the procedure through 7 days:

- Death
- Stroke
- Myocardial Infarction
- Diaphragmatic paralysis
- Transient Ischemic Attack (TIA)
- Cardiac Tamponade
- Pericarditis
- Pneumothorax
- Hospitalization or Emergency Room Visit
- Vascular Access Complication
- Heart Block
- Pulmonary Edema
- Pericardial Effusion resulting in pericardiocentesis or surgical intervention
- Thromboembolism

Major Complications during the procedure through 180 days:

- Pulmonary vein stenosis
- Atrio-esophageal fistula

Major Complication definitions can be found in **Appendix L** of this protocol. All Major Complications, as reported by the clinical investigator, will be reviewed and adjudicated by the Clinical Events Committee (CEC).

All adverse events will be documented and collected once the informed consent has been signed.

In the event of a study subject death, all possible efforts will be made to obtain relevant records from the hospital or the subject's primary care physician, including death certificates, to determine the cause of death.

5.3 Primary Effectiveness Endpoint

The primary effectiveness endpoint is chronic success. Chronic success is defined to be:

- Freedom from symptomatic atrial fibrillation, atrial flutter, and atrial tachycardia episodes from days 91 - 365 after the initial ablation procedure, as documented by event recording, ECGs, and Holter monitoring.
- No use of Class I, Class II, Class III or Class IV antiarrhythmic medications during days 91 - 365 after the initial ablation procedure with the following exceptions.
 - Addition of Anti- Arrhythmic (AAD) medication which was previously ineffective for AF and does not exceed the previous historical maximum dosage (24 hour total dose).
 - Use of Atrioventricular (AV) nodal blocking agents such as beta blockers (BB) and/or calcium channel blockers (CCB) that are maintained at the current dose (does not exceed previous historical maximum dosage (24 hour total dose).
- No more than two additional ablation procedures within 90 days of the initial ablation procedure and no additional ablation procedures after day 90.
- No use of a non-study device for ablation of any atrial fibrillation target. Commercially available non-study devices may be used for atrial flutter and atrial tachycardia ablation targets.
- No ablation of an atrial fibrillation target made by removing the ablation catheter from the Artisan catheter and manually manipulating the ablation catheter.
- Pulmonary vein isolation of at least 3 out of 4 veins confirmed by pulmonary vein entrance block during the last procedure within the blanking period.
- No surgical ablation for atrial fibrillation, atrial flutter, or atrial tachycardia within 90 days of the initial ablation.
- No direct current (DC) cardioversion for atrial fibrillation, atrial flutter, or atrial tachycardia within days 91 - 365 after the initial ablation procedure.
- No catheter or surgical ablation for atrial fibrillation, atrial flutter, or atrial tachycardia within days 91 - 365 after the initial ablation procedure.

5.4 Secondary Endpoints

- **Acute Procedural Success**

Acute procedural success is defined as the successful ablation of at least three of four pulmonary veins as shown by pulmonary vein entrance block per vein during the initial ablation procedure. A subject is considered to be an acute procedural failure if acute procedural success cannot be obtained by using the Hansen system and, as a result, manual manipulation is needed to complete the ablation procedure with the ablation catheter.

- **Chronic Safety**

Chronic safety is defined as the incidence of Major Complications during the period from 8 – 365 days following the initial ablation procedure (excluding pulmonary vein stenosis and atrio-esophageal fistula from 8 – 180 days, which are included in the

primary safety endpoint). The incidence of pulmonary vein stenosis and atrio-esophageal fistula is included during the period from 181 – 365 days.

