Secondary Endpoints	
Acute Procedural Success: Acute pulmonary vein isolation of at least three out of four veins, as documented by testing entrance block, during the procedure.
 
Chronic Safety: Incidence of Major Complications reported from day 8 through day 365.

Primary Hypothesis	
Safety: To determine if the Major Complication rate meets the pre-established target performance goal (TPG) of 16%. $H_0: \pi_s \geq 16\%$ vs. $H_1: \pi_s < 16\%$,
 
Effectiveness: To determine if the effectiveness rate meets the pre-established target performance goal (TPG) of 54%. $H_0: \pi_E \leq 54\%$ vs. $H_1: \pi_E > 54\%$,
 
Both primary hypothesis (Safety and Effectiveness) shall be met for study success.

Sample Size	The total sample size will be determined by a Bayesian adaptive design. The trial will enroll a minimum of 125 subjects and up to a maximum of 250 subjects. Interim analyses will be conducted starting after the first 125 subjects are enrolled, and continue every 25 subjects thereafter.
Subject Population	Subjects eligible for study participation must be diagnosed with symptomatic paroxysmal atrial fibrillation refractory to medical treatment, suitable for treatment with RF catheter ablation, meet all inclusion and no exclusion criteria and be willing to comply with all protocol testing and follow-up.
Inclusion Criteria:	
 1. Subjects with paroxysmal atrial fibrillation who have had two or more spontaneously terminating episodes of atrial fibrillation that last longer than 30 seconds and shorter than 7 days, in the nine months prior to enrollment. At least one episode must be documented with ECG, TTM, Holter monitor, or telemetry. 2. Failure of at least one Class I – IV anti-arrhythmic drug (AAD) for PAF as evidenced by recurrent symptomatic PAF, or intolerable side effects due to AAD. AADs are defined in Appendix B. 3. Signed informed consent. 4. Age 18 years or older. 5. Able and willing to comply with all pre-, post-, and follow-up testing and requirements.

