6.4 Secondary Effectiveness Endpoint – Acute Procedural Success

The secondary effectiveness endpoint is acute success of remotely introducing and positioning of commercially available ablation catheter through the Hansen system. The secondary effectiveness endpoint is defined as the rate of acute procedure success for at least three out of four pulmonary veins as shown by pulmonary vein entrance block per vein during the initial ablation procedure. A subject is considered to be an acute failure if acute procedural success cannot be obtained by using the Hansen system and, as a result, manual manipulation was needed to complete the ablation procedure.

The rate is estimated using proportions per subject. A one-sided 95% lower confidence level will be calculated for acute success rate. No hypothesis test will be performed for this secondary effectiveness endpoint.

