Remember that stable contact between the catheter tip and the tissue increases the efficiency of RF power transfer to the tissue.

For power levels up to 30W, a flow rate of 17 ml/min should be used (refer to the catheter Instructions for Use for specific recommendations for flow rate). If the temperature increases to greater than 50°C or the impedance rises 20Ω or more, the RF application should be terminated

immediately, the ablation catheter should be removed and the coagulum removed (if present), and irrigation flow confirmed before the catheter is used again.

- Verification of electrical PV isolation: A circular or basket catheter shall be used for verification of PV isolation by demonstrating entrance block for each pulmonary vein. Confirmation of PV isolation in at least 3 of 4 pulmonary veins must be achieved to meet the criteria for acute procedural success.
- A second structural cardiac echocardiogram (trans-thoracic, trans-esophageal, intra cardiac or IVUS) will be performed five minutes after the ablation catheter is removed from the subject to assess for the presence of a pericardial effusion. The time of this evaluation will be documented.
- Refer to the Hansen Medical Artisan IFUs and the ablation catheter IFU for more catheter use information.
 - It should be recorded in case report forms if it is not possible to safely complete treatment of a pulmonary vein due to proximity of the phrenic nerve or esophagus.
 - Additional optional ablation lesions shall be noted (for example: mitral isthmus, cavo-tricuspid isthmus, or non-pulmonary vein foci).
 - For every RF energy application, the following ablation information will be collected: force, power, impedance value, temperature, irrigation flow rate, and ablation duration. Refer to the case report forms for specific items.

Post-Procedural Care:

- Subjects will be monitored in the recovery room until stable per the investigative site's standard post-treatment procedures.

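### The acute-success rule in 5.4 and 6.4 turns on why manual work was done, so a third vein isolated manually by operator choice can be counted as a success of the Hansen system

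*Protocol*

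**What the plan says.** All references are to the protocol.

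- **Section 5.4** sets the success condition as "successful ablation of at least three of four pulmonary veins as shown by pulmonary vein entrance block per vein during the initial ablation procedure". Its only condition about the device is a failure clause, which applies when "acute procedural success cannot be obtained by using the Hansen system and, as a result, manual manipulation is needed to complete the ablation procedure".
- **Section 6.4** repeats both parts in nearly the same words; its failure clause ends with the condition that "manual manipulation was needed to complete the ablation procedure". It opens by stating the purpose: "The secondary effectiveness endpoint is acute success of remotely introducing and positioning of commercially available ablation catheter through the Hansen system". It plans a per-subject proportion with a one-sided 95% lower confidence limit, and no hypothesis test.
- **The synopsis** gives the endpoint as "Acute pulmonary vein isolation of at least three out of four veins, as documented by testing entrance block, during the procedure", with no clause on manual work.
- **Section 7.3.3**, in the step on verifying isolation, says: "Confirmation of PV isolation in at least 3 of 4 pulmonary veins must be achieved to meet the criteria for acute procedural success". It also directs that the ablation catheter be manipulated remotely.
- **Section 5.3** requires for chronic success: "No ablation of an atrial fibrillation target made by removing the ablation catheter from the Artisan catheter and manually manipulating the ablation catheter". That condition has no exception for the reason.

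**The concern.** The failure clause has two linked parts: the Hansen system could not deliver success, and manual work was required for that reason. An operator who finishes manually to save time, or from preference, meets neither part on a literal reading. If three veins then show block, the success condition is satisfied and nothing in 5.4 or 6.4 expressly removes the subject.

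The score for such a subject then depends on the treating operator's account of why the conversion happened, in an open single-arm study. The adjudication tasks listed for the Clinical Events Committee in 7.7 concern adverse events; none covers procedural success. At stake is whether the reported rate describes what the robotic system achieved, which is the purpose 6.4 gives for this endpoint.

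**Working it through.** The protocol states no acute-success figure, so there is nothing to reproduce. The check is on wording, followed by an illustration of size.

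**Step 1: apply the wording to four possible records.** All concern the initial procedure, with four veins targeted.

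| Record | 5.4 and 6.4 | Synopsis as worded | 5.3 manual-ablation condition |
|---|---|---|---|
| A. Three veins isolated through the Artisan, no manual work | Success | Success | Met |
| B. Two through the Artisan, system judged unable, two manual | Failure | Condition satisfied | Not met |
| C. Two through the Artisan, operator chooses to do two manually | Success condition satisfied; failure clause not triggered if read literally | Condition satisfied | Not met |
| D. Three through the Artisan, fourth manual | Success | Success | Not met |

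B and C are the same procedure with the same veins isolated by the same route. Under 5.4 and 6.4 only the stated reason separates them. The synopsis does not separate them at all. In C the Hansen system isolated two veins, which is short of the three required, yet the subject can be counted as a success.

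**Step 2: size, under assumed counts.** The inputs are:

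- n = 125 and n = 250, the minimum and maximum enrolment in 6.5, used as round denominators. The treated cohort may be smaller, because 6.5 expects 5% to be withdrawn before the procedure.
- k = number of subjects like record C. The protocol gives no value, so k is an assumption.
- All other subjects are taken as successes, also an assumption.
- The interval is the exact (Clopper-Pearson) one-sided 95% lower limit. The protocol does not name a method, so this too is assumed.

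With x = n − k successes, the lower limit is the 5% quantile of a Beta(x, n − x + 1) distribution. For x = n this reduces to 0.05^(1/n): 0.05^(1/125) = 0.976 and 0.05^(1/250) = 0.988.

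| n | k | Rate counting only Artisan-isolated veins | Lower limit |
|---|---|---|---|
| 125 | 0 | 125/125 = 100% | 97.6% |
| 125 | 3 | 122/125 = 97.6% | 93.9% |
| 125 | 6 | 119/125 = 95.2% | 90.7% |
| 125 | 12 | 113/125 = 90.4% | 84.9% |
| 250 | 0 | 250/250 = 100% | 98.8% |
| 250 | 5 | 245/250 = 98.0% | 95.8% |
| 250 | 12 | 238/250 = 95.2% | 92.3% |
| 250 | 25 | 225/250 = 90.0% | 86.3% |

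If every such subject were scored by the literal clause, each row would report the k = 0 result for its n. For k = 6 of 125 the lower limit would differ by 97.6 − 90.7 = 6.9 percentage points; for k = 12 of 250, by 98.8 − 92.3 = 6.5 points.

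**The case against.** The strongest reply is that 6.4 opens with the purpose, and the failure clause should be read in that light. In record C the Hansen system did not deliver three veins, and manual work was required to reach the third, so a reasonable scorer could call C a failure. That stands: the text permits the success score but does not compel it. A reader might infer that every version of the endpoint makes C a success, or that manual isolations are in fact credited to the robot. The documents support neither.

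Second, 7.3.3 directs remote manipulation, so elective manual isolation departs from the procedure and would be recorded as a deviation under 7.14. It also costs the subject the primary endpoint under 5.3. Operators thus have reason to avoid it, and the number of such cases may be zero. This limits the likely size. It does not settle the scoring, and both 5.3 and the failure clause foresee manual work.

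Third, it is tempting to treat 7.3.3 as a rival definition. It is not: its sentence states a condition that must be met, within a procedural step. The synopsis is different, since it presents itself as the endpoint and leaves the clause out, but it is an abbreviated statement.

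Fourth, a reader might see a contradiction between 5.3 and 5.4 because C can succeed on one and fail on the other. Acute and chronic success are different endpoints and may differ. The comparison shows only that the protocol elsewhere uses a rule that does not depend on the reason.

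Finally, the analysis plan or case report forms may say how conversions are coded; neither is shown. That could resolve C in practice, but the protocol's own wording would still rest on the operator's reason.

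**Conclusion.** The point holds as an ambiguity with a direction. As written, 5.4 and 6.4 allow a subject with fewer than three veins isolated through the Hansen system to be counted as an acute success when the manual work was elective, and the synopsis drops the clause altogether. Any resulting error would raise the reported rate.

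The effect is confined to the reported acute success rate and its one-sided 95% lower limit. This endpoint is not tested, and no performance goal, power figure, stopping rule or study-success criterion uses it. The sizes shown rest wholly on assumed conversion counts and on all other subjects succeeding; they are not evidence that the rate will be inflated. The change is still worth making, because it replaces a judgement about motive with an observable fact at little cost.

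**What to change.** In 5.4 and 6.4, and repeated in the synopsis, count toward acute success only veins isolated at the initial procedure with the ablation catheter manipulated through the Artisan catheter. Score as acute failure any subject in whom fewer than three veins were isolated that way, whatever the reason for any manual or non-study-device ablation. The sentence in 7.3.3 can stay as a necessary condition.

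This should not be described as the same rule as the 5.3 condition. In record D, manual ablation of a fourth vein after three were isolated through the Artisan, the subject would remain an acute success and a chronic failure. That difference is acceptable if stated.

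The cost is a wording change in three places and a possibly slightly lower reported acute rate. Whether any AF target was ablated manually must already be known to score 5.3. For subjects with such ablation, the route must also be known vein by vein, so the sponsor should confirm that the procedure form captures it. The change concerns scoring only and places no new limit on what operators may do.
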